11.1.7 Other Considerations

Abbreviated Title: Ad5-based combination vaccines
Version Date: 05.16.2018

The Ad5 [E1-, E2b-] vector is non-replicating and its genome does not integrate into the human genome. However, since this is a non-replicating recombinant virus, it is recommended that it be handled under Biosafety Level-2 conditions. Any vial of ETBX vaccine material that has been used in the study should be autoclaved or incinerated after use according to institutional policy and according to local, state and federal regulations. Refer to the Material Safety Data Sheets for additional handling instructions.

13 APPENDICES

13.1 APPENDIX A: PERFORMANCE STATUS CRITERIA

ECOG Performance Status Scale		Karnofsky Performance Scale	
Grade	Descriptions	Percent	Description
0	Normal activity. Fully active, able to carry on all pre-disease performance without restriction.	100	Normal, no complaints, no evidence of disease.
		90	Able to carry on normal activity; minor signs or symptoms of disease.
1	Symptoms, but ambulatory. Restricted in physically strenuous activity, but ambulatory and able to carry out work of a light or sedentary nature (e.g., light housework, office work).	80	Normal activity with effort; some signs or symptoms of disease.
		70	Cares for self, unable to carry on normal activity or to do active work.
2	In bed <50% of the time. Ambulatory and capable of all self-care, but unable to carry out any work activities. Up and about more than 50% of waking hours.	60	Requires occasional assistance, but is able to care for most of his/her needs.
		50	Requires considerable assistance and frequent medical care.
3	In bed >50% of the time. Capable of only limited self-care, confined to bed or chair more than 50% of waking hours.	40	Disabled, requires special care and assistance.
		30	Severely disabled, hospitalization indicated. Death not imminent.
4	100% bedridden. Completely disabled. Cannot carry on any self-care. Totally confined to bed or chair.	20	Very sick, hospitalization indicated. Death not imminent.
		10	Moribund, fatal processes progressing rapidly.
5	Dead.	0	Dead.

13.2 APPENDIX B: INJECTION SITE REACTIONS DIARY CARD

Please answer all questions below once per day for the first 7 days

		Day 0 (Day of Injection)	Day +1	Day +2	Day +3	Day +4	Day +5	Day +6
1. Is there redness at the injection site?	Circle: Yes / No If yes measure longest diameter in millimeters (mm)	Yes / No _____mm						
2. Is there firmness or swelling at the injection site?	Circle: Yes / No If yes measure longest diameter in millimeters (mm)	Yes / No _____mm						
3. Is there soreness at the injection site?	Circle: Yes / No If yes tell us if the soreness is mild, moderate, or severe	Yes / No Mild Moderate Severe						
4. Have you experienced pain at the injection site?	Circle: Yes / No If yes tell us if the pain is mild, moderate, or severe	Yes / No Mild Moderate Severe						
5. Have you taken any medication for	Circle: Yes / No Provide name and	Yes / No Name: _____						

		Day 0 (Day of Injection)	Day +1	Day +2	Day +3	Day +4	Day +5	Day +6
injection site pain?	dose of medication	Dose: _____						
6. Have you experienced chills?	Circle: Yes / No If yes tell us if the chills are mild, moderate, or severe	Yes / No Mild Moderate Severe						
7. Record your daily temperature (Do not drink anything within 5 minutes prior to taking your temperature)	Circle: Yes / No If your temperature is 104°F for more than 24 hours, call your study doctor	Record Temp: _____

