1.2.8 Clinical Experience

The combination of ETBX-011, ETBX-061, and ETBX-051 vaccine has not been tested in humans.

This Phase I study is the first clinical study of this vaccine combination in subjects with advanced cancer.

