3.1.1 Dose Limiting Toxicity

For the purposes of dose escalation a dose limiting toxicity (DLT) is defined as:

- Any Grade 3 or greater toxicity that is possibly related to the vaccine and as defined by Common Terminology Criteria for Adverse Events (CTCAE) Version 5.0 with the exception of transient (≤ 24 hours) Grade 3 flu-like symptoms or fever, which is controlled with medical management or transient (≤ 24 hours) Grade 3 fatigue, skin reactions or rash, headache, nausea, emesis that resolves to Grade ≤ 1 or asymptomatic grade 3 amylase/lipase elevation. For purposes of dose escalation the DLT evaluation period will be for 3 weeks following the first dose of drug.

Subjects experiencing a DLT will be removed from protocol therapy.

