3.1.2 Dose De-Escalation

Up to six patients will be enrolled at dose level 1. If ≤ 1 of 6 patients experience a DLT, initiation of the dose expansion phase will occur. If ≥ 2 of 3 or 6 experience DLT in the initial dose level, then dose de-escalation will occur. Up to six patients will be enrolled at the lower dose level (-1) (1×10^{11} VP). If ≤ 1 of 6 patients experience a DLT, then the maximum tolerated (MTD) will be declared at this dose, and initiation of the dose expansion phase will occur. If ≥ 2 of 3 or 6 experience DLT at dose level -1, then an amendment may be written to evaluate a further dose de-escalation.

In the second part, dose expansion will occur when the MTD has been determined. An additional 4 subjects will be enrolled in the dose expansion component of the trial, for a total of 10 subjects treated at the MTD.

A schematic overview of the study is shown in Figure 6.

In the initial component of the study, 3 to 6 subjects will be sequentially enrolled starting at the standard dose at dose level 1. During enrollment at each dose level, there will be a minimum of 3 days between enrolling successive subjects. DLTs will be monitored continuously.

Dose levels are shown in Table 4. No intra-patient dose escalations are permitted.

Table 4: Dose Levels for Each ETBX VP

Dose Level (DL)	ETBX VP
Standard (1)	5×10^{11}
-1	1×10^{11}

[figure not shown]
Standard dose (DL 1) (5×10^{11} VP):

- If ≤ 1 of the initial 6 subjects experience a DLT, dose expansion will commence.
- If >1 of the initial 3 subjects, or if ≥ 2 of the 6 total subjects experience a DLT, enrollment at DL -1 will commence.

Dose de-escalation DL -1 (1×10^{11} VP):

- If ≤ 1 of the initial 6 subjects experience a DLT, this dose level will be defined as the MTD and dose expansion will commence.
- If >1 of the initial 3 subjects, or if ≥ 2 of the 6 total subjects experience a DLT, then a protocol amendment may be written to evaluate a further dose de-escalation..

Figure 6: Study Design and Treatment Schema

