3.6 INJECTION SITE REACTIONS

Local injection site reactions are expected to occur over several days after vaccination. Erythema and some soreness are possible. Injection site reactions will be monitored by clinic staff prior to discharge and by subject self-evaluation and reporting. Subjects will be given a diary card with reporting fields for diameter of erythema and duration for the seven days after the first set of vaccine injections (see [Appendix B](#)). In addition, pain at the injection site, fever, and chills will be collected as Yes/No and medications (over-the-counter ibuprofen, acetaminophen, aspirin, etc.) taken for injection site pain or discomfort as Yes/No. The site staff will review the diary cards with the subject during the next clinic visit and record responses in the case report form.

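### The diary card asks subjects to call only after more than 24 hours at 104°F; it should ask for a call at the first such reading

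*Combined protocol and SAP*

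**What the plan says.** Appendix B is headed as an injection-site reaction diary. Its general instruction is "Please answer all questions below once per day for the first 7 days", with columns from Day 0 to Day +6. Item 7 asks for the daily temperature and, in the text as read, gives one entry field for it. There is no field for the clock time, or for when a fever began or ended. The only instruction to contact anyone is "If your temperature is 104°F for more than 24 hours, call your study doctor".

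Section 3.6 describes the card's use after the first set of injections. It says that "pain at the injection site, fever, and chills will be collected as Yes/No", and on review it says "The site staff will review the diary cards with the subject during the next clinic visit". The study calendar (Section 3.5) hands the card out at baseline and reviews it at Week 3, with no visit or telephone contact scheduled between them.

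Section 1.2.8 states: "This Phase I study is the first clinical study of this vaccine combination in subjects with advanced cancer". Section 3.1.1 leaves out of the DLT definition "transient (≤ 24 hours) Grade 3 flu-like symptoms or fever, which is controlled with medical management", and adds: "Subjects experiencing a DLT will be removed from protocol therapy". Section 3.1.2 says: "DLTs will be monitored continuously".

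**The concern.** A call instruction on a card kept at home tells the subject when the site wants to hear from them. This one sets that moment after a full day at 104°F. The combination has not been given to people before, and the study population has advanced cancer, so the first day of a high fever is when the site would want to assess the subject and start treatment. The plan schedules no other contact until Week 3. What is at stake is the timing of medical contact for an individual subject.

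There is a lesser point about documentation. One untimed reading a day cannot show whether a fever lasted more or less than 24 hours, and the fever exemption in Section 3.1.1 uses that limit.

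**Working it through.** The plan gives no figure to reproduce. The check is how long after fever onset the card would prompt a call, now and under the proposed wording.

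**Inputs.** One reading a day for seven days and a trigger of more than 24 hours at 104°F (Appendix B); review at Week 3 (Sections 3.5 and 3.6). Assumptions: one continuous fever, onset equally likely at any hour, long enough to be read, and only the requested readings taken.

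**Call timing, same clock time each day.** Let U be the hours from onset to the next reading, uniform on 0 to 24.
- First febrile reading: U, range 0–24 h, mean 24/2 = 12 h.
- Second febrile reading, the earliest that can span 24 h: U + 24, range 24–48 h, mean 36 h.
- Gain from calling at the first reading: 36 − 12 = 24 h.

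**Call timing, reading times varying between 08:00 and 22:00** (simulation of 400,000 fevers).
- The first febrile reading averages 12.7 h after onset and falls within 24 h in 90% of cases.
- The second averages 36.0 h. The gain is 36.0 − 12.7 = 23.3 h.

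**What the readings say about duration (secondary).** For k consecutive febrile readings between non-febrile ones:

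| k | Same clock time: 24(k−1) to 24(k+1) h | Untimed: max(0, 24(k−2)) to 24(k+2) h |
|---|---|---|
| 1 | 0 to 48 | 0 to 72 |
| 2 | 24 to 72 | 0 to 96 |
| 3 | 48 to 96 | 24 to 120 |

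One or two untimed readings cannot place a fever on either side of 24 h. At a fixed time, an 18-hour fever leaves exactly one febrile entry with probability 18/24 = 0.75. A 30-hour fever does so with probability 1 − 6/24 = 0.75. A single entry therefore does not separate the two.

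**Extra calls.** Section 11.1.2 lists 9 fevers of any grade in 94 treatments with the CEA vaccine alone: 9/94 = 9.6% per treatment. That row's attribution counts sum to 6 + 1 + 4 = 11, so 9 is approximate. Section 8.2 plans 6–12 subjects for dose finding plus 4 more, which gives 10–16 first doses.
- At the single-vaccine rate: 10 × 9/94 = 0.96 to 16 × 9/94 = 1.53 fevers.
- If three vaccines tripled the rate (assumption): 2.9 to 4.6.

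These are fevers of any grade. Calls triggered at 104°F would be fewer.

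**The case against.** The best case for the card is that it is an injection-site diary and not the only safety channel. It sets a point at which the subject must call and does not discourage calling sooner. Contact and consent pages, where such instructions often sit, are not in the text provided. Item 7 also looks damaged as read: it has a Yes/No to circle but no matching question, so a lost field cannot be ruled out. A subject judging whether 104°F has lasted a day may well take more than one reading. All of this limits how firmly one can say that no earlier contact is asked for. It does not change what the card's own instruction says, and a stricter rule elsewhere would conflict with the card the subject holds at home. Frequent readings do not rescue the wording either, because a subject who follows it literally still waits more than 24 hours.

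A reader might go further and infer that the card leaves DLTs misclassified and so threatens the dose decision. The documents do not support that. They cite CTCAE version 5.0 but give no fever cut-off, so it cannot be confirmed from them that 104°F is Grade 3. Adverse event records are to hold start date, stop date and duration (Section 8.4.4). Adverse events are followed until they resolve or stabilise (Section 6.1), DLTs are monitored continuously (Section 3.1.2), and the research team discusses each patient weekly (Section 7.6.1). The exemption also requires that the fever be controlled by treatment, so a fever cannot become exempt merely because its duration is unclear. These provisions do not guarantee timing to the hour, but they make an unresolved fever less likely.

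High fever may also be rare. Section 11.1.2 lists no Grade 3 or 4 fever among 34 patients, and one case (1/34 = 2.9%) would have met the table's 2% limit. That is limited reassurance, since only six of those patients received the present dose, and of one vaccine rather than three.

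**Conclusion.** The point holds for the call instruction. As read, Appendix B does not ask a subject for contact during the first day at 104°F. Asking at the first such reading would bring the prompted call forward by about 24 hours (23 to 24 hours under the two reading patterns examined). This rests on the card as extracted and on subjects following it; it needs no assumption about fever grading. Other call instructions may exist in the removed pages.

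The 24-hour exemption in Section 3.1.1 is a secondary matter. Timed readings would help document whether a fever met the limit, if 104°F corresponds to Grade 3, which the documents do not confirm. No effect on the dose decision is claimed. This is a cheap improvement for the sponsor to consider, with medium confidence.

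**What to change.** Reword item 7 of Appendix B so that the subject calls the study doctor at the first reading at or above 104°F, or at a lower threshold that the sponsor chooses. Add the clock time to each temperature entry, and ask for a repeat timed reading when febrile. Section 3.6, which describes fever as a Yes/No item, should then be aligned with the card. Check that any call instruction in the consent and contact material agrees.

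The cost is a revised card, a conforming sentence in Section 3.6, slightly more effort for subjects in the first week, and a few extra calls. Nothing changes in the design, sample size or analysis.
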